**17. Statistical Considerations:**

- a. Sample Size Calculations:** A target of 138 subjects will be targeted, with 69 in each group. This is based on the assumption, with 80% power, that 25-30% of the subjects in the SD group will achieve a protective titer compared to 50-60% of the HD-TIV group for at least one influenza antigen. Accounting for a 20% drop out rate, 138 subjects will be recruited.

Strain	Expected Seroprotection HD-TIV	Expected Seroprotection SD-QIV	N (HD)	N (SD)	Power	Total N with 20% drop out
Expected HD-TIV seroprotection is twice as of SD-QIV						
A	40%	20%	80	80	80%	200
A	50%	25%	55	55	80%	138
A	60%	30%	40	40	80%	100
A	70%	35%	28	28	80%	70

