- b. Immunogenicity analysis:** The probability of achieving a 4-fold (or greater) rise in post-vaccination HAI titers relative to baseline, as well as the probability of a HAI titer greater than 1:40, will be estimated using a binomial model, using the full analysis set. We will calculate the Bayesian posterior distribution of the probabilities under all 4 combinations of SD- and HD-TIV crossed with a single dose and two doses. From these probabilities, odds ratios will be calculated along with 95% credible intervals. These quantities will be modeled as a logit-linear function of several covariates, including CD4+/CD8+/CD19+, and IgG/IgM levels, absolute neutrophil and lymphocyte count (or their ratio), time from post-transplant to enrollment, type of preparative regimen, donor status, and stem cell source. We will use normal priors with standard deviation of 5 for all logit-linear coefficients and the baseline mean, which are not informative when transformed to the probability scale. Scale (standard deviation) parameters will be given long-tailed half-Cauchy priors, also in the interest of being uninformative. In addition, the distributions of geometric mean HAI titers for high and SD-QIV recipients will be estimated via log-normal models, and expressed as ratios in order to evaluate the evidence for higher GMT in the HD-TIV sample, after one and two vaccines. The scale parameters for priors under the log-normal model will be increased by an order of magnitude relative to the logit-linear models to ensure that they do not influence the posterior estimates. We will compare each group to document if they meet serological criteria by WHO biological standards for influenza vaccines (>40% for seroconversion, GMT >2.5-fold increase, and >70% with ≥1:40). Subjects with missing data will be excluded from the analysis, but the sensitivity of the results to missingness will be formally analyzed by comparing posterior estimates under the range of possible outcomes for the missing individuals.
- c. Safety analysis:** For the primary analysis of the safety data, the proportion of subjects in each group (using full analysis set) experiencing at least one solicited AE will be calculated along with 95% posterior credible intervals. The difference between the rates of solicited AEs between the

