groups will be estimated by calculating the posterior 95% credible interval of the difference in proportions. For continuous-valued events (e.g. size of swelling) uninformative priors will be used as described in (17.b); for discrete events, a flat beta parameter with scale=shape=1 will be used as uninformative priors. For each group and each event, solicited and unsolicited AEs will be descriptively summarized. Severities of solicited and unsolicited AEs will also be descriptively summarized for each group and each type of event. Descriptive statistics will include number experiencing event, mean and 95% posterior credible interval. Maximum size of redness and swelling may be descriptively summarized for each group and event; proportion of events lasting longer beyond Day 3 may also be descriptively summarized. Subjects with missing data will be excluded from analysis, but the sensitivity of the results to missingness will be formally analyzed by comparing posterior estimates under the range of possible outcomes for the missing individuals.

- d. Influenza-Like-Illness assessment:** The percentage of individuals in each group that test positive for influenza by PCR and the number of ILIs in each group during the influenza season will be compared.

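### Excluding subjects with missing data from an undefined full analysis set can discard usable titres, and the planned sensitivity range has no criterion for robustness

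*Combined protocol and SAP*

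**What the plan says.** Section 17.b fits a binomial model to the full analysis set for the four-fold rise and the 1:40 titre, covering both arms after one and after two doses. Log-normal models are added for the geometric mean titres. The response probabilities are regressed on CD4, CD8, CD19, IgG, IgM, neutrophil and lymphocyte counts (or their ratio), time since transplant, preparative regimen, donor status and stem cell source. The section then states: "Subjects with missing data will be excluded from the analysis, but the sensitivity of the results to missingness will be formally analyzed". The sensitivity check compares posterior estimates across the outcomes that the missing subjects could have had. Section 17.c repeats the rule for safety: "Subjects with missing data will be excluded from analysis". The full analysis set is named in both sections and defined in neither.

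Section 17.a gives the sample size: "Accounting for a 20% drop out rate, 138 subjects will be recruited". The row of its table behind the target reads "A 50% 25% 55 55 80% 138".

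**The concern.** A full analysis set that then loses everyone with missing data is in effect a complete-case set, and its membership depends on what counts as missing. The candidates are the baseline titre, either post-dose titre, or a covariate. Two statisticians could follow the text and analyse different subjects.

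Three things are at stake:

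- **Discarded information.** Sections 8.b and 13 ask sites to obtain post-immunisation samples even from withdrawn subjects, so partial data will exist. A subject with a Visit 2 titre but no Visit 3 titre, or with both titres but no IgM, has data that the literal rule throws away.
- **Possible bias.** Relapse is an exclusion criterion (section 4.b), and meeting an exclusion criterion may lead to discontinuation (section 8.a). Those who leave may respond differently from those who stay. The documents do not allow the direction of any bias to be stated.
- **No rule for reading the sensitivity analysis.** Nothing says which part of the range counts, or what result would be called robust.

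**Working it through.** **Inputs.** From section 17.a: 50% versus 25%, 55 evaluable per arm, 80% power, 20% drop-out, 138 in total. From section 5: 1:1 allocation, 69 per arm. The documents state no significance level. I assume two-sided 5%, in line with "odds ratios will be calculated along with 95% credible intervals".

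**1. The plan's own figure.** With unpooled variance, n = [0.50 x 0.50 + 0.25 x 0.75] x (1.960 + 0.842)² / 0.25² = 54.94, so 55 per arm. Then 55 / 0.8 = 68.75, so 69 per arm and 138 in total. The figure reproduces.

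**2. What the allowance covers.** 69 x 0.8 = 55.2. Exclusion at exactly the planned 20% keeps the powered number, with essentially no reserve for other exclusions.

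**3. Further loss if a missing covariate excludes a subject.** The seven laboratory covariates come from three tests: blood count with differential, CD4/CD8/CD19, and IgG/IgM. Section 17.b does not say at which visit they are taken; I assume Visit 1. The missing rates m are also assumed. Remaining n = 55 x (1 - m)³, and power = Φ(0.25 / √(0.4375 / n) - 1.96).

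| Missing rate per test | n per arm | Power |
|---|---|---|
| 2% | 51.8 | 78% |
| 3% | 50.2 | 76% |
| 5% | 47.2 | 74% |
| 5%, all three tests lost together | 52.2 | 78% |

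**4. The sensitivity range at the planned loss.** Take 14 of 69 missing per arm (20.3%), with observed responses of 28/55 and 14/55. Independent Beta(1,1) posteriors without covariates serve as a simplified stand-in for the planned model.

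| Missing subjects | High dose | Standard dose | Odds ratio (95% credible interval) |
|---|---|---|---|
| Excluded | 28/55 | 14/55 | 2.95 (1.35-6.66) |
| All fail | 28/69 | 14/69 | 2.62 (1.26-5.62) |
| All succeed | 42/69 | 28/69 | 2.25 (1.15-4.46) |
| High-dose missing respond at the standard-dose rate | - | - | 2.41 (1.20-4.93) |
| Best corner | 42/69 | 14/69 | 5.88 (2.84-12.73) |
| Worst corner | 28/69 | 28/69 | 1.00 (0.51-1.96) |

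Without rounding to whole subjects, the worst corner is 27.5/69 = 39.9% against (13.75 + 14)/69 = 40.2%. Over all 15 x 15 = 225 combinations of missing outcomes, the interval excludes 1 in about 148. In the plan's 60% versus 30% scenario, the worst corner is 33/69 versus 30/69, odds ratio 1.19 (0.61-2.32).

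**5. Lower missingness, 50% versus 25%.** With 4 missing per arm (5.8%), the worst corner still excludes 1: 2.09 (1.05-4.24). With 5 per arm it no longer does: 1.95 (0.98-3.92).

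**The case against.** The strongest reply is that the rule most naturally concerns missing outcomes, because the sentence goes on to vary the outcomes of the missing subjects, and a subject without an IgM value still has a known outcome. On that reading the 20% inflation covers the loss. This is a fair reading, but the text does not state it, and it does not settle what happens to a subject with only one of the two post-dose titres.

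A reader might infer four stronger points that the documents do not support:

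- **That the analysed number falls below 55 at the planned drop-out.** It does not, since 55.2 remain.
- **That missingness multiplies over all eleven listed covariates.** Time since transplant determines eligibility and the randomisation stratum. Regimen, donor and cell source are transplant-history items. The laboratory values share one draw, so gaps would cluster.
- **That only extremes are checked, so robustness cannot be shown.** The planned range includes intermediate cases, most of which keep the interval above 1. At low missingness even the worst corner does.
- **That the two doses are modelled as independent.** The text names no subject-level term, but it also says "Scale (standard deviation) parameters will be given long-tailed half-Cauchy priors" while describing the logit-linear model. A plain binomial-logit model has no such parameter, so a hierarchical term may be intended. The issue would in any case bear on the one-dose versus two-dose contrast, not on the primary comparison of vaccines.

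The plan also limits loss by seeking samples from withdrawn subjects and by allowing local laboratory draws for Visit 3 where distance is a problem (section 14).

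**Conclusion.** The point holds as a cheap improvement to the stated method. The full analysis set is undefined, and the exclusion rule read literally discards usable titres. Any exclusion on top of 20% drop-out takes the analysed number below the powered 55. The size is modest: about 47-52 per arm and 74-78% power if each of three laboratory tests is missing in 2-5% of subjects. Those rates, independence between tests, and a two-sided 5% level with unpooled variance are assumptions. Bias from loss related to relapse or illness is possible but is not shown.

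The sensitivity analysis is reasonable in scope and lacks a decision rule. At the planned loss its odds ratios run from 1.00 to 5.88, and nothing says which part of that range would count for or against the result.

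**What to change.** For immunogenicity, amend section 17.b as follows:

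1. Define the full analysis set as randomised, vaccinated subjects with at least one post-vaccination titre.
2. Fit the dose 1 and dose 2 results in one model with a subject-level term, so that an observed titre after one dose informs a missing one after the other. The half-Cauchy prior already stated can serve for its scale.
3. Treat missing titres and missing baseline covariates as unknowns in the Bayesian model instead of deleting the subject, and state the visit from which covariates are taken.
4. Within the range already planned, pre-specify an arm-specific tipping-point criterion: how far the response odds of missing subjects must shift in each arm before the credible interval includes 1, and which shifts are considered plausible.

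In section 17.c, define the safety set separately and say which missing data lead to exclusion.

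The cost is revised text and more model code, with no added subjects, visits or samples. The main estimate would rest on a missing-at-random assumption, which the tipping-point analysis tests.

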## A. Specific Aims and Hypothesis:

1. **Hypothesis 1:** *We hypothesize that the high dose trivalent inactivated influenza vaccine (HD-TIV) group will have a greater frequency of  $\geq 4$ -fold rise and HAI titer  $\geq 1:40$  and higher geometric mean titer (GMT) to influenza A antigens compared to the standard dose quadrivalent inactivated influenza vaccine (SD-QIV) group.*

**Specific Aim #1:** To determine whether HD-TIV compared with SD-QIV will increase the probability of achieving either a  $\geq 4$ -fold rise in HAI titer, a HAI titer  $\geq 1:40$ , or a higher GMT to influenza A antigens in adult HSCT recipients.

2. **Hypothesis 2:** *We hypothesize that HD-TIV will be well tolerated, with a safety profile similar to SD-QIV.*

**Specific Aim #2:** To determine the frequency and severity of solicited local injection site adverse events and solicited systemic adverse events related to HD-TIV compared with SD-QIV in adult HSCT recipients.

3. **Hypothesis 3:** *We hypothesize that HD-TIV vaccination will induce higher protective HAI titers and higher frequencies of circulating activated T-follicular (Tfh) cells and circulating B cell plasmablasts, it will also induce higher levels of influenza-specific B and T cell responses compared to SD-QIV.*

**Specific Aim #3:** To define the relationship between HAI titers, *in vivo* T and B cell phenotype, and *in vitro* influenza-specific T and B cell responses in adult HSCT recipients receiving either HD-TIV or SD-QIV.

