### b. Secondary Objectives:

- i. To determine whether HD-TIV compared with SD-QIV will increase the probability of achieving a  $\geq 4$ -fold rise in HAI titers,  $\geq 1:40$  HAI titer, or higher GMT titers to influenza B antigens in adult HSCT recipients.
- ii. To determine the frequency and severity of solicited local injection site adverse events (e.g. pain/ tenderness, redness, and swelling/induration at injection site) with HD-TIV compared to SD-QIV in adult HSCT recipients.
- iii. To determine the frequency and severity of solicited systemic adverse events (e.g. fevers, headache, fatigue/malaise, nausea, body ache/myalgia, general activity level, and vomiting) with HD-TIV compared to SD-QIV in adult HSCT recipients.
- iv. To define the relationship between HAI titers, *in vivo* T and B cell phenotype, and *in vitro* influenza-specific T and B cell response in adult HSCT recipients receiving either HD-TIV or SD-QIV.
- v. To correlate HAI responses to MN responses.
- vi. To compare the persistent HAI and MN titers for all four antigen seven months after the last vaccine dose to assess for persistence of antibody titers.
- vii. To compare influenza detection by PCR during influenza season in adult HSCT recipients receiving either HD-TIV or SD-QIV.
- viii. To assess HAI and MN response in patients (e.g. repeaters) undergoing two-consecutive years revaccination using the same antigen dose
- ix. To correlate HAI responses to neuraminidase inhibition titers (NAI).

**3. Study Area:** The study will be conducted in the Oncology Units or Clinics, or Clinical Trial Centers at the following sites: **Table 2** includes the yearly average number of transplants per site.

Table 2. Clinical Sites	Average Number of Yearly Allogeneic Transplants
Northwestern University Feinberg School of Medicine	167
Fred Hutchinson Cancer Research Center	300
University Hospital, University of Alabama at Birmingham	90
Vanderbilt University Medical Center	108
TOTAL	665

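### The primary safety comparison pools solicited reactions of every grade and type, and no HD-minus-SD difference is clearly pre-specified for severity or for local versus systemic reactions, although Aim 2 asks for both

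*Combined protocol and SAP*

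**What the plan says.** Section 17.c names one primary safety variable: the proportion of subjects in each group "experiencing at least one solicited AE will be calculated along with 95% posterior credible intervals". No grade threshold is attached, and local and systemic reactions are not separated. The difference in rates of solicited AEs between the "groups will be estimated by calculating the posterior 95% credible interval of the difference in proportions". For discrete events, "a flat beta parameter with scale=shape=1 will be used as uninformative priors".

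Severity comes later in the same section: "Severities of solicited and unsolicited AEs will also be descriptively summarized for each group and each type of event". The next sentence gives the content of those summaries: "Descriptive statistics will include number experiencing event, mean and 95% posterior credible interval". Individual events are also summarised by group. No margin, posterior-probability threshold or other decision rule is stated.

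Specific Aim #2 reads: "To determine the frequency and severity of solicited local injection site adverse events and solicited systemic adverse events related to HD-TIV compared with SD-QIV". The matching hypothesis is: "We hypothesize that HD-TIV will be well tolerated, with a safety profile similar to SD-QIV". Secondary objective ii begins "To determine the frequency and severity of solicited local injection site adverse events". Objective iii is its systemic counterpart, and each is framed as HD-TIV against SD-QIV. Tables 4 and 5 (Section 16.e) define Grades 1 to 3 for each symptom, local and systemic in separate tables.

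**The concern.** The stated aims have two dimensions that the primary variable lacks: how severe a reaction was, and whether it was local or systemic. A subject with Grade 1 tenderness on one evening counts the same as a subject with a Grade 3 systemic reaction. The variable draws on eleven solicited items (four local, seven systemic) recorded over Days 0 to 7 after each of two doses.

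Two results would then be hard to interpret. An interval around zero could coexist with a real shift towards moderate and severe reactions. An interval above zero could come entirely from mild injection-site reactions, which the sponsor's earlier HSCT trial gives reason to expect: Section B.4.a reports more local symptoms with the high dose and no systemic difference. Because Hypothesis 2 is that the profiles are alike, an insensitive main comparison leans towards the hypothesised answer.

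**Working it through.** **Sample size available.** Section 17.a is the only planning figure that fixes the numbers for safety. For 50% versus 25%, with 80% power and an assumed two-sided 5% level (the section states none), the unpooled formula gives n = (1.96 + 0.8416)² × [0.50×0.50 + 0.25×0.75] / 0.25² = 7.849 × 0.4375 / 0.0625 = 54.9, so 55 per arm. Then 110 / 0.8 = 137.5, so 138 in total. Both agree with the plan. Safety is therefore examined with between 55 and 69 subjects per arm.

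**Method.** With x events among n subjects and a Beta(1,1) prior, each arm's posterior is Beta(1 + x, 1 + n − x). The 95% interval for HD minus SD lies wholly above zero when the posterior probability that the HD rate is at or below the SD rate is under 0.025. That probability was computed for every pair of counts, and the pairs that meet the condition were weighted by their binomial probabilities under the assumed true rates.

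**Assumed rates.** The documents give none for any solicited AE or for Grade 2 or higher. The nearest figure is 10–64% for injection-site soreness alone (Section 11.a). All rates below are illustrations.

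| Variable | SD vs HD | Above zero, n = 69 | Above zero, n = 55 |
|---|---|---|---|
| Any AE, equal | 70% vs 70% | 2% | 2% |
| Any AE, similar | 80% vs 85% | 12% | 9% |
| Any AE, moderate rise | 70% vs 80% | 26% | 22% |
| Any AE, strong rise | 70% vs 90% | 85% | 76% |
| Grade 2 or higher | 10% vs 30% | 85% | 76% |
| Grade 2 or higher | 5% vs 15% | 50% | 38% |
| Grade 2 or higher | 3% vs 9% | 27% | 19% |

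Estimating the posterior limits by random draws moves the 69-per-arm figures by about a point (11% for 80% versus 85%, 86% for 10% versus 30%). It moves the 55-per-arm figures by up to about five points (43% for 5% versus 15%).

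**Two worked data sets at 69 per arm.**

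1. Any AE in 48 versus 48: difference 0.00 (−0.15 to 0.15). Grade 2 or higher in 21 (HD) versus 7 (SD): difference 0.20 (0.07 to 0.33). The by-arm intervals already planned are 0.21–0.42 and 0.05–0.20. They do not overlap, so a reader would see this excess.
2. Grade 2 or higher in 10 versus 3: difference 0.10 (0.002 to 0.202), just above zero. The by-arm intervals are 0.08–0.25 and 0.02–0.12, which overlap. Here the by-arm summaries do not give the reader the comparison that the difference interval gives.

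**The case against.** The strongest reply is that Section 17.c has to be read whole. It summarises each event, and the severity of each type of event, by arm with 95% credible intervals, so severity and reaction type are reported. A reader might infer that the plan ignores severity. It does not. What is missing is a specified difference between arms, and the second data set above shows that separate intervals are no substitute for one.

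A reader might also infer that the plan would declare no difference while moderate and severe reactions tripled. The documents do not support that. They set no decision rule, so the output is an interval and not a verdict. Nor is the pooled variable blind to every such change: if the any-grade rate rises along with the higher grades, it responds. The contrast of 12% with 85% depends on rates chosen so that any-grade incidence barely moves.

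The sentence on differences speaks of rates in the plural, and the next sentence sets priors for continuous measures such as swelling size. The difference may therefore be meant for each event. On that reading individual local and systemic symptoms are already compared. That reading is possible, but it still gives no pooled local or pooled systemic contrast and nothing on grade. The ambiguity is itself a reason to clarify.

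Finally, Grade 3 events have their own reporting and halting provisions (Sections 7, 16.a and 16.j), and the DSMB may see data by arm. These protect subjects during the trial. They do not supply the final comparison that Aim 2 describes.

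**Conclusion.** The point holds as a gap between the aims and the specified comparisons. The primary safety contrast pools all grades and types. No HD-minus-SD difference is specified for severity, and none clearly for local or systemic reactions, although Aim 2 and objectives ii and iii ask for both against SD-QIV.

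The size of the loss is conditional. Where any-grade rates are close, the planned contrast has little chance of signalling a change in severity that a graded contrast would show with good probability at 69 per arm. Where any-grade rates separate widely, the pooled contrast detects the excess but cannot say whether it is mild or severe, local or systemic. A graded contrast is no cure at low base rates: at 5% versus 15% it shows the excess in half the trials or fewer. All of this rests on illustrative event rates. The textual gap does not.

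**What to change.** Keep the any-AE comparison in Section 17.c. Add, with the same Beta(1,1) priors and the same 95% credible interval for the HD-minus-SD difference in proportions:

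- any local solicited AE, and any systemic solicited AE;
- within local and within systemic, each subject's maximum grade from Tables 4 and 5, as the proportion at Grade 2 or higher, with Grade 3 also reported.

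State in the same place whether the existing difference sentence covers only the any-AE composite or each event as well.

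The cost is wording and a few more intervals from memory-aid data that are already collected and graded. No further subjects, visits or models are needed. The drawback is that several safety contrasts must be reported together, and those for rare Grade 3 events will have wide intervals.
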